Mobile Physical Activity for Type 1 Diabetes

NCT04204733

March 23, 2021

Statistical Analysis plan

Data will be exported from the Web API, Actilife, and REDCap and merged into an SPSS 24.0 (Armonk, NY) database for analysis. Each variable will be described with frequency distributions and appropriate summary statistics for central tendency and variability; these univariate analyses will help to assess assumptions underlying the statistical tests used in the analysis.

**Primary Aim 1a. To examine the feasibility of a mobile diabetes self-management application and tools to promote physical activity (PA) in patients with type 1 diabetes (T1D).** Feasibility of the mobile intervention will be evaluated according to standards set by previous in-person T1D self-management interventions:

- a) **Enrollment**, defined as proportion of eligible patients who are approached that complete the consent process and baseline assessments. Standard is 50%.
- b) **Retention**, defined as the proportion of patients completing the baseline assessments that also complete the follow-up assessments. Standard is 90%.
- c) **Biosensor adherence**. For CGM, this is defined as the proportion of possible readings obtained assuming a sampling every 5min. Standard is 98%. For accelerometry, this is defined as the proportion of subjects wearing the device  $\geq 4$  days  $\geq 10$ hr/day. Standard is 92%.

In addition, mobile product usability will be evaluated based upon the System Usability Scale where a score  $\geq 70$  is considered acceptable.

**Primary Aim 1b. To estimate the probable magnitude of the pre-post effect on PA and clinical and mental health outcomes that may be improved by PA.** Pre-post effect on each outcome will be estimated using Cohen's formula (0.20 considered small, 0.50 medium, 0.80 large).

**Secondary Aim. To evaluate predictors and mechanisms of PA behavior change.** This aim will be analyzed by a mixed methods approach. The quantitative dependent variable will be momentary classification of PA status based upon accelerometry, mobile diaries, and timeline followback (TLFB) according to intensity (sedentary, light, moderate, or vigorous) and type (aerobic, resistance, neuromotor, flexibility). Analysis will focus on three primary objectives: 1) To develop a machine learning model that will classify PA status with at least 80% accuracy, 2) To determine the appropriate duration of observation needed to build a model with at least 80% accuracy in predicting future PA, and 3) To determine the classification accuracy of the model trained on group-level data and tested on individual-level data. Modeling frameworks we will apply include: elastic net penalized cox proportional hazards regression, logistic time-varying effect models, and Bayesian multistate Markov models with interval-censored data. Demographics (e.g., age, sex, race/ethnicity), baseline health profile (e.g., body composition, depression), momentary usage of each intervention component, and momentary values of other external (e.g., location, time of day) and internal (e.g., blood glucose, insulin on board, fear of hypoglycemia (FOH)) will be evaluated as potential predictors. Possibilities of time-lagged prediction will be tested (e.g., afternoon PA could be influenced by a morning teleconsultation), particularly for FOH which is only assessed twice daily. These quantitative results will be combined with qualitative results from exit interviews by a mixed methods approach according to Sekhon's theoretical framework for acceptability to determine intervention components that are most helpful and influential regarding PA behavior change.

**Data Sharing.** Individual deidentified participant data (including data dictionaries) will be shared. This includes individual participant data that underlie the results reported in any aspect of a published article (text, tables, figures, and appendices). Other documents that will be

available include the study protocol, statistical analysis plan, informed consent form, analytic code. The data will be available immediately following publication with no end date. Data will be shared with researchers who provide a methodologically sound proposal to achieve aims in the approved proposal. Proposals should be directed to [name] at Yale University ([[contact]](mailto:[contact])). To gain access, data requesters will need to sign a data access agreement.

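### Does 90% retention put the 98% CGM standard out of reach, and do bare percentages undermine the feasibility verdict?

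*SAP*

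**What the plan says.** SAP, Primary Aim 1a, introduces its criteria as benchmarks: "Feasibility of the mobile intervention will be evaluated according to standards set by previous in-person T1D self-management interventions". Four of them matter here.

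- Enrollment, item a): "defined as proportion of eligible patients who are approached that complete the consent process and baseline assessments. Standard is 50" percent.
- Retention, item b): "defined as the proportion of patients completing the baseline assessments that also complete the follow-up assessments. Standard is 90" percent.
- CGM adherence, item c): "this is defined as the proportion of possible readings obtained assuming a sampling every 5min. Standard is 98" percent.
- Accelerometry, item c): "For accelerometry, this is defined as the proportion of subjects wearing the device" on at least 4 days for at least 10 hours a day, with a standard of 92%.

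Items a) and b) name their denominators. The CGM item gives only the sampling interval. It does not say which participants or days make up the possible readings, or whether the percentage is pooled or averaged over participants. The accelerometry item does not say over what period the 4 days are counted. The section plans no confidence intervals and no rule that combines the standards into one verdict.

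**The concern.** Aim 1a is a primary question, and its standards come from different cited studies, so it is fair to ask whether one trial can meet them all. Read literally, the possible CGM readings could be every 5-minute slot for every participant over the whole monitoring period. Dropout would then count as non-adherence, and a loss of participants that item b) accepts could by itself cause a failure on item c). Accelerometry looks similar: if it were judged at follow-up over all baseline completers, 90% retention would cap it at 90%, below its 92% standard.

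A second worry is precision. Each standard is compared with an observed percentage, and in a small study that percentage is uncertain. If both worries held, a program with good wear and acceptable retention could be reported as infeasible, or the reverse.

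**Working it through.** The SAP states no sample size, power or interval, so there is no design figure to reproduce. The inputs from Primary Aim 1a are retention R = 0.90, CGM standard 0.98 at one reading per 5 minutes, accelerometry standard 0.92 and enrollment standard 0.50. All values of N below are assumptions.

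**1. What 98% allows.** One reading per 5 minutes gives 288 a day. The tolerated loss is 0.02 × 288 = 5.76 readings, or 28.8 minutes a day.

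**2. CGM ceiling if all baseline completers count for the full period.** Let c be capture while in the study and f the average share of possible readings lost by a non-retained participant. Then

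ceiling = c × [1 − (1 − R) × f].

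With R = 0.90 and c = 1:

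| f | Ceiling |
|---|---|
| 1 | 90% |
| 0.50 | 95% |
| 0.25 | 97.5% |
| 0.20 | 98% |
| 0.10 | 99% |
| 0 | 100% |

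The break-even value is f = (1 − 0.98/c)/(1 − R). It is 0.20 at c = 1, about 0.10 at c = 0.99 and 0 at c = 0.98. The two standards are therefore incompatible on this denominator only under enough early loss. Because retention depends on the follow-up assessments, a participant can miss those and still have supplied nearly all CGM readings (f close to 0).

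**3. CGM ceiling if only days in the study count.** The factor (1 − R) × f drops out and the ceiling is c, whatever the retention. Time with the sensor off still counts against adherence; time after leaving does not.

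**4. Accelerometry.** The 90% cap needs three conditions: wear judged only at follow-up, all baseline completers in the denominator, and no wear from those who miss follow-up. Item c) states none of them. The Secondary Aim uses accelerometry to classify activity from moment to moment, so wear confined to follow-up cannot be assumed.

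**5. Bare percentages.** Exact binomial results for the rule that observed retention is at least 90%:

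| Assumed N | Needed | Misses if truth is 90% | Meets if truth is 80% | Exact 95% CI at the count needed |
|---|---|---|---|---|
| 20 | 18 | 32.3% | 20.6% | 68.3% to 98.8% |
| 30 | 27 | 35.3% | 12.3% | 73.5% to 97.9% |
| 50 | 45 | 38.4% | 4.8% | 78.2% to 96.7% |
| 100 | 90 | 41.7% | 0.6% | 82.4% to 95.1% |

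The misses at a true 90% do not shrink as N grows. They come from placing the truth exactly on a cut-off, not from a small sample. The chance of passing a program 10 points below the standard does fall with N, and even at 30 the rule separates 80% (passes 12.3%) from 90% (passes 100% − 35.3% = 64.7%). The other standards behave in the same way at 30. Enrollment misses 42.8% at a true 50% and meets 17.5% at a true 40%. Accelerometry misses 43.5% at a true 92% and meets 7.4% at a true 82%.

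**6. A rule based on intervals.** Suppose a standard counts as met only when the exact 95% interval lies wholly at or above it. With perfect data the lower limit is 0.025^(1/N), which at N = 30 is 88.4%. Perfect data would clear 90% only if N ≥ ln 0.025 / ln 0.90 = 35.0, rounded up to 36. They would clear 92% only if N ≥ ln 0.025 / ln 0.92 = 44.2, rounded up to 45.

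**The case for a change.** The best argument for a change is that the SAP itself defines these measures and gives explicit denominators for enrollment and retention, but not for CGM. The same data could then pass or fail a primary benchmark according to a choice made after they are seen. On a pooled count with equal possible readings per participant, one person with no readings costs 1/N, which exceeds the 2% allowance whenever N is below 50. Clarifying the text would cost a sentence or two, and intervals would show how little a small study can settle.

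The gap is real, and a report should state the denominator used. Exact intervals beside each proportion would also be good practice. But the obvious reading, capture over each participant's own days in the study, already fits the text and keeps dropout in the retention measure where item b) puts it. Monitoring length and wear schedule are commonly set in the protocol, which is not shown here. A low pooled figure would miss one benchmark, not fail the trial, because the SAP has no combined verdict. Intervals can be added at reporting without amending the plan. A met, not met or inconclusive rule is a debatable exchange: it guards against false reassurance, but in a study of 30 it would leave no possible result that meets the retention or accelerometry standard.

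**Conclusion.** No change to the plan follows. The standards do not contradict each other. They are separate minimum benchmarks, and a trial at 90% retention can still reach 98% CGM capture. The shortfall appears only if all baseline completers are counted for the full period and non-retained participants lose more than 20% of their readings on average, with capture otherwise complete. In that case it ranges up to 8 points (98% − 90%). The accelerometry cap likewise rests on a timepoint and a denominator that the SAP does not state.

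What is left is missing detail that analysts can fill sensibly: whose days count for CGM, and over what window the 4 accelerometer days fall. Intervals would describe precision but would change no estimate and no comparison with a standard. A pass rule built on them is a trade-off on which statisticians may reasonably differ. The precision figures rest on assumed N of 20 to 100, since the SAP gives none. The conclusion about the CGM standard does not depend on N.

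### Aim 1b estimates every pre-post effect with Cohen's formula and names no small-sample correction, so effects are overstated slightly: by 1.6% to 9.4% for normal outcomes with 50 down to 10 pairs

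*SAP*

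**What the plan says.** Primary Aim 1b is one of estimation: "To estimate the probable magnitude of the pre-post effect on PA and clinical and mental health outcomes that may be improved by PA". The SAP gives one rule for it: "Pre-post effect on each outcome will be estimated using Cohen's formula". The estimate is then graded: "0.20 considered small, 0.50 medium, 0.80 large".

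No small-sample correction is named, and the SD that serves as divisor is not identified. Nothing is said about the scale of analysis, either to require the raw scale or to allow a transformation. The opening paragraph plans descriptive summaries of each variable and adds that "these univariate analyses will help to assess assumptions underlying the statistical tests used in the analysis". It attaches no consequence for Aim 1b to what those summaries show. The document gives no sample size, no SDs and no outcome distributions.

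**The concern.** Cohen's d is a mean change divided by a sample SD. The mean change is unbiased, but the reciprocal of a sample SD is on average too large, so d is too far from zero, and more so the fewer the pairs. The direction of this bias is known and, for normal outcomes, so is its size.

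The standardised effect is the stated estimate of a primary aim, and it is compared with fixed cut-offs. An estimate that runs high leans towards the higher label. It also leads to an undersized later trial if one is planned from it, because the required sample size varies as 1/d². Strong right skew can enlarge the excess, since a small sample often misses the tail that makes up much of the SD.

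**Working it through.** **Inputs.** From the SAP: the estimator (Cohen's formula, divisor not named) and the cut-offs 0.20, 0.50 and 0.80. Assumed, because the SAP does not give it: n = 10 to 50 complete pairs. There is no figure in the plan to reproduce.

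**Normal outcomes, change SD or baseline SD.** Under normality the sample means are independent of the sample SDs, and either SD carries df = n - 1. The inflation is therefore

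E[d]/δ = √(df/2) · Γ((df - 1)/2) / Γ(df/2),

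and its reciprocal is closely approximated by Hedges' factor J = 1 - 3/(4·df - 1).

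| Pairs n | df | J | Inflation (exact) | d = 0.50 after correction |
|---|---|---|---|---|
| 10 | 9 | 1 - 3/35 = 0.914 | +9.4% | 0.46 |
| 20 | 19 | 1 - 3/75 = 0.960 | +4.2% | 0.48 |
| 30 | 29 | 1 - 3/115 = 0.974 | +2.7% | 0.49 |
| 50 | 49 | 1 - 3/195 = 0.985 | +1.6% | 0.49 |

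**Normal outcomes, pooled SD.** Averaging the pre and post variances raises the effective df to about 2(n - 1)/(1 + r²), where r is the pre-post correlation. With r = 0.7 (assumed) and n = 20 this is 38/1.49 = 25.5, so the factor is 1 - 3/(4 × 25.5 - 1) = 0.970 and the inflation about 3.1%. Applying J with df = n - 1 then over-corrects slightly: 0.960/0.970 = 0.989, about 1% low. At n = 10 the same steps give df 18/1.49 = 12.1, factor 0.937 and 0.914/0.937 = 0.976, about 2% low. A simulation agrees (inflation 2.9% and 6.6%). It also confirms that J with df = n - 1 removes the bias for the change-SD and baseline-SD versions.

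**Consequences of the normal-case bias.**
- Labels: at n = 20 the average estimate is pushed over the 0.50 cut-off only if the true value lies between 0.48 and 0.50; at n = 10, between 0.46 and 0.50.
- Precision: for the change-SD version at n = 20 and d = 0.50, the standard error is about √(1/20 + 0.25/40) = 0.24, against a bias of 0.50 × 0.042 = 0.02.
- A later trial sized from the uncorrected d would be too small by 1 - J²: 16% at n = 10, 8% at n = 20 and 3% at n = 50.

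**Right-skewed outcomes, illustration only.** Assumed: lognormal pre and post values analysed untransformed, correlation 0.7, a log-scale shift of 0.35 SD and n = 20. The table gives the excess of the mean estimate over its own population value, before and after multiplying by J.

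| Log-SD | Pooled SD | Change SD | Baseline SD |
|---|---|---|---|
| 0.8 | 13% → 9% | 14% → 10% | 33% → 28% |
| 1.0 | 21% → 16% | 24% → 19% | 54% → 48% |

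Hedges' factor depends only on n, so it removes about 4 to 6 points of this excess. The figures depend heavily on the assumptions. Across other plausible choices of n, skewness, correlation, divisor and type of effect, the excess ran from about 2% to over 200%.

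**The case against.** The strongest reply is that the part needing no assumption about skew is small. At 20 to 50 pairs a d of 0.50 becomes 0.48 or 0.49, well inside its sampling error, and an uncorrected d is a conventional descriptive effect size in a feasibility study. This stands as to size and is why the point is graded minor. It does not make the bias harmless to leave in, since its direction is known and its removal costs almost nothing.

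Two stronger readings are tempting, and the document does not support them.

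- **That the plan overstates skewed outcomes by some set amount, such as 13% to 55%.** A reader might infer this from the skewed illustration. That range belongs to one lognormal scenario at n = 20, spread over three divisors. The SAP gives no n, distribution, correlation or divisor, and it does not commit to the raw scale. Nor did the mean estimate change label in any of the 27 cells examined with the 0.35 log-scale shift (three skew levels, n of 20, 30 and 50, three divisors). Both it and the population value stayed between 0.20 and 0.50. The closest was baseline SD at log-SD 1.0 and n = 20, where 0.32 became 0.49 on average.
- **That skewed outcomes should therefore be moved to the log scale.** That switch changes the quantity estimated to a ratio of geometric means, so it is not a bias correction. It does not generally lower d either. In the same illustration at n = 20 the log-scale d averages 0.36 (pooled SD) and 0.47 (change SD), against 0.32 to 0.35 and 0.34 to 0.43 on the raw scale.

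It may also be objected that the n - 1 factor is not exact for every divisor. It is right for the change SD and the baseline SD. With the pooled SD it over-corrects by about 1% at 20 pairs and 2% to 3% at 10.

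**Conclusion.** The point holds in a limited form. Aim 1b names Cohen's formula with no small-sample correction. For normal outcomes this overstates the effect by 9.4%, 4.2%, 2.7% and 1.6% at 10, 20, 30 and 50 pairs with the change or baseline SD, and by somewhat less with the pooled SD. The figures rest on normality and on an assumed number of pairs; with more than 50 pairs the matter is negligible.

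For a strongly right-skewed outcome the excess may be larger, and the correction would remove only part of it. Whether any outcome here is that skewed, and by how much its effect would be inflated, cannot be settled from the SAP. Severity: minor, for consideration.

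**What to change.** In Primary Aim 1b, state that each pre-post effect will be reported as the bias-corrected effect (Hedges' g). This is d multiplied by 1 - 3/(4(n - 1) - 1), with n the number of complete pairs for that outcome, and it is the value compared with 0.20, 0.50 and 0.80.

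Optionally, if the baseline distribution shows an outcome to be strongly right-skewed, give a pre-post ratio from the log scale alongside the corrected effect as a sensitivity result, not as a replacement. Decide this before follow-up values are seen.

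The cost is one sentence and one line of code, with no new data. The downside for the sponsor is that reported effects become slightly smaller.

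### The 80% accuracy target in Secondary Aim objectives 1 and 2 is not tied to the commonest class's share, so a model without skill meets it if that share is 80% or more

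*SAP*

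**What the plan says.** The Secondary Aim defines its outcome as "momentary classification of PA status based upon accelerometry, mobile diaries, and timeline followback (TLFB"), graded "according to intensity (sedentary, light, moderate, or vigorous) and type (aerobic, resistance, neuromotor, flexibility").

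Two of its three objectives carry the same numeric threshold. Objective 1 is to develop a model "that will classify PA status with at least 80% accuracy". Objective 2 is to find the length of observation "needed to build a model with at least 80% accuracy in predicting future PA". Objective 3 reports an accuracy but sets no threshold.

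The frameworks named are "elastic net penalized cox proportional hazards regression", "logistic time-varying effect models" and "Bayesian multistate Markov models with interval-censored data".

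Accuracy is not qualified anywhere, so its plain meaning, the proportion classified correctly, applies. The SAP gives no majority-class baseline, no balanced or chance-corrected measure, no per-class measure and no expected class shares. Its opening paragraph does say "Each variable will be described with frequency distributions", but the accuracy criterion makes no use of those distributions.

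**The concern.** A fixed accuracy threshold has meaning only relative to what can be scored without using any predictor. Because the outcome is momentary, ordinary time between bouts of activity may be scored along with the bouts, and one class may dominate. If it holds 80% or more of the scored moments, objective 1 can be declared met by a model that identifies no activity at all.

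Objective 2 is more exposed, because there the threshold acts as a selection rule. A constant prediction needs almost no data to learn, so it would meet the target at the shortest observation length tried. The duration reported as appropriate would then reflect the base rate and not what the model had learned.

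**Working it through.** **Inputs**
- Target: accuracy of at least 0.80 (SAP, Secondary Aim, objectives 1 and 2). This is a chosen threshold, so there is no derivation to reproduce.
- Classes: four intensity levels and four types (same section). Whether intensity, type, their combination or a binary split is scored is not stated.
- Class shares: not given. They are assumed below over a range.
- Scored minutes per day: not given. 600, 900 and 1440 are assumed. The 10 hours per day under Primary Aim 1a is an accelerometer wear standard, not a scoring denominator.

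**Step 1: accuracy of the constant rule.** Let s be the share of the commonest class. Always predicting that class is correct in a proportion s of moments, so its accuracy is s. Its sensitivity for every other class is 0.

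| s | Constant-rule accuracy | Meets 80%? | Gain over the constant rule of a model at exactly 80% (0.80 − s) |
|---|---|---|---|
| 0.50 | 50% | no | +30 points |
| 0.70 | 70% | no | +10 points |
| 0.79 | 79% | no | +1 point |
| 0.80 | 80% | yes | 0 |
| 0.85 | 85% | yes | −5 points |
| 0.90 | 90% | yes | −10 points |

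The rule passes exactly when s ≥ 0.80, whatever the number of classes.

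**Step 2: what the target demands when s is below 0.80.** Let x be the proportion correct within the commonest class and y the proportion correct among all other moments. Accuracy is s·x + (1 − s)·y. Since x cannot exceed 1, reaching 0.80 requires y ≥ (0.80 − s)/(1 − s).
- s = 0.60: 0.20/0.40 = 50% of the other moments must be classified correctly
- s = 0.70: 0.10/0.30 = 33.3%
- s = 0.75: 0.05/0.25 = 20%
- s = 0.79: 0.01/0.21 = 4.8%
- s = 0.80: 0%

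So the target is a real test when s is well below 0.80, and it loses its force as s approaches 0.80.

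**Step 3: illustration under an assumed active/not-active coding.** If not-active is the commoner class, predicting it throughout has accuracy 1 − (active minutes/scored minutes). In 600 scored minutes:
- 30 active: 1 − 30/600 = 95%, passes
- 60 active: 90%, passes
- 90 active: 85%, passes
- 120 active: 80%, passes
- 150 active: 75%, fails

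The break-even is 0.20 × 600 = 120 minutes. For 900 and 1440 scored minutes it is 0.20 × 900 = 180 and 0.20 × 1440 = 288. Whether light intensity would count as active is not stated, and that choice shifts the active share.

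**Step 4: can the document settle s?** No. Cox and logistic models can take a two-state outcome, while a multistate Markov model fits several states, so the listed frameworks do not fix the coding. The four types contain no category for inactivity, so scoring type at every moment would need a residual class, whose share is also unknown. The three data sources do not fix the number of scored moments per day.

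**The case against.** The strongest reply is that nothing shows the problem arises here. Every share above is assumed, the worked illustration uses a two-class coding that the SAP does not write, and the caution applies to any accuracy target. That is correct, and it is why the point is conditional. A reader might infer that sedentary or inactive time must exceed 80%, so that the target is empty in this trial, or that naming a Cox and a logistic model implies a binary outcome. The document supports neither: it gives no shares, and the multistate framework and four intensity levels point equally to several classes.

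A second reply is that the aim exists to evaluate predictors, so a model that used none would be noticed, and the promised frequency distributions may reveal any imbalance. This limits the harm, but the stated criterion would still be satisfied on its own terms.

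A third is that the coding, the validation scheme and the per-class reporting may be in a protocol that is not at hand. Their absence alone would be no finding. However, the performance criterion itself is written into the SAP, twice, without a comparator, so how it is fixed can fairly be examined.

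**Conclusion.** The point holds as a conditional and minor one. The 80% target is met without skill if and only if the commonest scored class holds 80% or more of the scored moments. Whether it does cannot be determined from the SAP. Under an assumed two-class coding and 600 scored minutes, the condition is met with up to 120 active minutes. Where the commonest share is well below 80%, the target is informative and little is lost.

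The consequence is confined to objectives 1 and 2, and is greatest for objective 2. Objective 3 has no threshold. It would be wrong to infer that the feasibility or effect-size results of Primary Aims 1a and 1b are weakened: neither uses this criterion, and the SAP ties no go/no-go decision to the 80%.

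**What to change.** In the Secondary Aim:

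1. State which coding of PA status is scored for each objective.
2. Keep the 80% target and add, for objectives 1 and 2, that accuracy on held-out data must also exceed the majority-class accuracy in the same held-out data. The lower 95% limit of the difference, from a bootstrap that resamples participants, should lie above 0.
3. For objective 2, take the shortest observation length that meets both conditions.
4. Report majority-class accuracy, balanced accuracy, per-class sensitivity and the confusion matrix beside raw accuracy.

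The comparator should be the base rate itself, because requiring only that balanced accuracy exceed chance would not be enough. With an assumed 10% active share, sensitivity of 10% and specificity of 98%, raw accuracy is 0.10 × 0.10 + 0.90 × 0.98 = 89.2% and balanced accuracy is (0.10 + 0.98)/2 = 54%, above the chance value of 50%. Yet the constant rule scores 90%, and the model misses 90% of active moments. Under condition 2 it fails.

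The cost is SAP wording and a modest amount of programming, with no new data. Reported success may be less favourable. When one class is very common the base rate is hard to beat, so a failure must be read together with the per-class results.

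### Does the 80% accuracy target in the Secondary Aim need a stated rule that keeps a tested participant's data out of training?

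*SAP*

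**What the plan says.** All the relevant text is in the Secondary Aim of the SAP.

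- **Outcome.** "The quantitative dependent variable will be momentary classification of PA status", built from accelerometry, diaries and timeline followback. Each participant therefore supplies many rows.
- **Objective 1.** A model "that will classify PA status with at least 80% accuracy".
- **Objective 2.** The length of observation needed to "build a model with at least 80% accuracy in predicting future PA".
- **Objective 3.** The accuracy of "the model trained on group-level data and tested on individual-level data".
- **Candidate predictors.** Demographics, then "baseline health profile (e.g., body composition, depression), momentary usage of each intervention component", and other momentary values. The first two groups are constant within a person.
- **Search.** Three modelling frameworks are named: penalised Cox regression, logistic time-varying effect models and Bayesian multistate Markov models. The list is not closed. On lags: "Possibilities of time-lagged prediction will be tested".

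The SAP mentions no hold-out set, cross-validation scheme, unit of split or tuning rule.

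**The concern.** A numeric accuracy target means little until one knows which data are scored. Two features of this aim make that matter. Rows repeat within person, and some predictors are fixed for a person, so in combination they can act as an identifier. If one person's rows fall in both training and test data, a model can learn that person's usual activity level from those fixed values and look accurate without having learned anything that carries over to someone else. Choosing among frameworks and lags on the same data would add further optimism, which was not quantified.

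At stake is the reading of the 80% target. Two analysts could score the same data differently, and one might report the target met while the other does not. If objective 3 were scored with shared participants, its figure would not be the accuracy for an unseen individual.

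**Working it through.** **1. Nothing to reproduce.** The 80% is a goal. The SAP gives no sample size, number of moments, class frequencies or between-person variation, so every numerical input below is an assumption.

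**2. What each objective estimates.**
- Objective 1 concerns classification of PA status and says nothing of new patients. If the target is accuracy at a fresh moment in this cohort, a row split answers that question. Only scoring on the fitted data would be wrong on every reading.
- Objective 2 is about the future, so it implies a split by time, and using a person's own past is legitimate.
- Objective 3 sets training data against test data. Its natural reading is a group model applied to individuals.

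**3. Size in a binary simulation.** The person intercept is normal with standard deviation SD on the logit scale. Latent ICC = SD²/(SD² + 3.29):
- SD 1: 1/4.29 = 0.23
- SD 2: 4/7.29 = 0.55
- SD 3: 9/12.29 = 0.73

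Other inputs: 20, 30 or 50 participants, 100 moments each, 6 person-constant and 2 momentary predictors, 5 folds. Ridge logistic regression is a rough stand-in for the listed penalised regression. A random forest represents a flexible model, which the SAP neither lists nor excludes. The time-varying effect and Markov models were not simulated.

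*All predictors noise, SD 1 to 3:*

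| Model | Row split | Participants held out | Gap (points) |
|---|---|---|---|
| Ridge | 55–68% | 48–52% | 6–19 |
| Forest | 65–83% | 48–51% | 16–35 |

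Only the forest at SD 3 passes 80% on noise (82–83%).

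*One real momentary predictor, forest, 30 participants, log-odds 1.5, 2 and 2.5 per SD of the predictor:*

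| Person SD | Participants held out | Row split |
|---|---|---|
| 1 | 68%, 73%, 77% | 74%, 78%, 81% |
| 2 | 60%, 65%, 69% | 79.9%, 82%, 83% |

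At SD 1 the gaps are 74 − 68 = 6, 78 − 73 = 5 and 81 − 77 = 4 points, and only the strongest predictor crosses 80%. At SD 2 they are 79.9 − 60 = 19.9, 82 − 65 = 17 and 83 − 69 = 14 points, and two of the three cross.

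*One real predictor, ridge, SD 1 and 2:* the gap is 1 to 11 points. Row splitting crosses 80% only where held-out accuracy is already 79 to 80%.

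**4. Smaller differences between people.** Further runs used 30 participants with 100 rows each, and one momentary predictor at log-odds 2 or four at log-odds 1:
- SD 0 (forest): the two scorings agree within 1 point.
- SD 0.5 (latent ICC 0.25/3.54 = 0.07): gap at most 1 point for both models.
- SD 1: gap about 3 points for ridge and 3–4 for the forest; neither passes 80% by row split.
- SD 2: ridge gap 5–7 points, with 73–74% by row split; forest gap 13–14 points, with 81% by row split.

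**5. Four classes and in-sample scoring.** The SAP's outcome has several classes, so a 5-nearest-neighbour classifier was run on four classes, with 30 participants, 40 rows each and 8 replicates:

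| Person SD | In-sample | Row split | Participants held out |
|---|---|---|---|
| 0 | 62.9% | 50.3% | 49.1% |
| 1 | 67.1% | 55.3% | 40.3% |
| 2 | 76.2% | 67.4% | 35.2% |
| 3 | 81.6% | 74.6% | 34.2% |

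In-sample scoring is optimistic even at SD 0 (62.9 − 49.1 = 13.8 points). Row splitting is optimistic only when people differ: 50.3 − 49.1 = 1.2 points at SD 0, against 55.3 − 40.3 = 15.0 at SD 1. Row splitting never reaches 80% here; in-sample scoring does so only at SD 3.

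**The case for a change.** The best argument for a change is that the SAP itself fixes the target, outcome, predictors, frameworks and lag search, so the data to be scored belong in the same place and cannot be left to a protocol. Objective 1 has no wording to fall back on. Flexible classifiers are not ruled out, because it speaks of machine learning in general and cites a general machine learning library. A remedy would take a few sentences and no new data.

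Much of this stands. The silence is real, a validation scheme normally sits in an SAP, and in-sample scoring would be optimistic in every setting tried. With a forest and SD 2 the overstatement is large.

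What does not stand is the step from silence to error. The SAP does not call for in-sample or row-wise scoring. The new-patient benchmark is not in objective 1, and objective 3 reads most naturally as a group model carried to individuals. The largest gaps come from noise-only predictors with flexible models that the SAP does not list.

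**Conclusion.** No change follows. The SAP leaves a gap that analysts competent to fit these models would be expected to fill sensibly, by scoring on data not used for fitting and by keeping the tested person out of the group model in objective 3. Naming the unit of split when reporting would be a useful clarification, but nothing in the plan is wrong without it.

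For penalised regression with a real predictor the difference is about 1 to 11 points and hardly moves the 80% verdict. With a random forest it can reach 20 points at SD 2 and change the verdict. At SD 1 it is 4 to 6 points in the main runs and changes the verdict only with the strongest predictor. These figures rest on assumed numbers of participants, moments, predictors and heterogeneity; they show direction and possible size, not this trial's bias.

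The consequences are also limited. Primary Aims 1a and 1b rest on enrollment, retention, biosensor adherence, usability and pre-post effect sizes, none of which uses model accuracy. The SAP attaches no decision to meeting 80%; the quantitative results are combined with exit interviews. Its Data Sharing section also makes deidentified participant data and analytic code available, so requesters with an approved proposal could check how accuracy was scored.
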